6.8.4 Variable selection

We will fit models that include all predictor variables initially and retain variables if they have a hazard ratio of < 0.90 or > 1.10 (for binary variables) and are statistically significant at the 0.01 level. For previous diagnoses of other cancers, we will retain variables which were significant at the 0.05 level since some of the cancers are rare. In order to simplify the models, we will focus on variables for the most common conditions and medications and combine similar variables with comparable hazard ratios where possible. If some predictor variables result in very sparse cells (i.e. with not enough participants or events to obtain point estimates and standard errors), we will combine some of these if clinically similar in nature.

For PPI and H2 blockers medication usage, we will determine the association between risk of oesophageal cancer and type of medication (omeprazole etc), dose and duration of exposure (e.g. < 6 months; 6-11 months; 12-23 months; 24-47 months; 48 months or more). We will examine both usage at baseline and also as a time varying exposure during study follow-up.

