6.3 Study period

Patients will enter the cohort on the latest of the study start date or the date on which they become 25 or 12 months after registering with their GP practice. Patients will be followed up until they develop oesophageal cancer, die, leave the practice or the study end date or a maximum follow up period of 15 years.

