6.6.1 Demographic variables

- 1. Age (continuous variable)*.
- 2. Townsend deprivation score*. This is an area-level continuous score based on the patients' postcode³⁰. Originally developed by Townsend³⁰, it includes unemployment (as a percentage of those aged 16 and over who are economically active); non-car ownership (as a percentage of all households); non-home ownership (as a percentage of all households) and household overcrowding. These variables are measured for a given area of approximately 120 households, via the 2011 census, and combined to give a "Townsend score" for that area. A greater Townsend score implies a greater level of deprivation.
- 3. Ethnicity (9 categories)

6.6.2 concurrent medication (at study entry)

- 1. Proton pump inhibitors (which are used to treat reflux symptoms)
- 2. H2 blockers (which are used to treat reflux symptoms)
- 3. NSAIDs (which can worsen reflux symptoms)
- 4. Aspirin (which may lower OAC risk)^{14 16}
- 5. Statins (which may lower OAC risk)^{17 31}
- 6. COX inhibitors (which may lower OAC risk)¹⁷
- 7. Metformin (which may lower OAC risk)¹⁵
- 8. HRT (in female only, may lower OAC risk)¹⁵
- 9. Other diabetic drugs

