6.6.4 Co-morbidities and investigations

- 8. gastric cancer
- 9. Barrett's oesophagus*
- 10. Peptic ulcer disease*
- 11. Gastro-oesophageal reflux disease (including heart burn)
- 12. Type 1 and type 2 diabetes*
- 13. previous blood cancer*
- 14. previous breast cancer*
- 15. previous oral cancer*
- 16. previous pancreatic cancer*
- 17. Current H.Pylori infection (which may lower OAC risk)
- 18. pernicious anaemia
- 19. hiatus hernia
- 20. anaemia (including Haemoglobin values)
- 21. Full blood count
- 22. CT scan abdomen within the previous 5 years
- 23. CT scan pelvis within the previous 5 years
- 24. Barium meal/swallow within the previous 5 years
- 25. Endoscopy within the previous 5 years

All predictor variables will be based on the latest coded information recorded in the GP record prior to entry to the cohort.

6.7 **Descriptive analysis**

We will produce the following descriptive analyses for comparison with the literature and national statistics from the CRUK website.

- crude incidence of oesophageal cancer by age, sex, ethnicity, deprivation and calendar time.
- age standardised incidence of oesophageal cancer overall and by type.
- characteristics of cases diagnosed with oesophageal cancer age at diagnosis, stage, grade, histology, treatment (surgery, radiotherapy, chemotherapy, other).

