6.8.3 Handling of missing data

For all predictor variables, we will use the most recently available value at the time origin. For indicators of co-morbidities and medication use, the absence of information being recorded is assumed to mean absence of the factor in question. There may be missing data in some variables due to never being recorded: ethnicity, Townsend score, body mass index, smoking status and alcohol intake. We will use multiple imputation with chained equations to replace missing values for these variables ³⁶⁻³⁹.

Prior to the imputation, a complete-case analysis will be fitted using a model containing only the continuous covariates within the derivation data to derive the fractional polynomial order and corresponding powers. Then a multiple imputation model using chained equations will be fitted in the derivation data and will include all predictor variables along with age interaction terms, the Nelson–Aalen estimators of the baseline cumulative hazard, and the outcome indicators (namely, oesophageal cancer). Separate imputation models will be fitted for men and women. We will carry out 5 imputations as this has a relatively high efficiency²⁹ and is a pragmatic approach accounting for the size of the datasets and capacity of the available servers and software.

Each analysis model will be fitted in each imputed data set. We will use Rubin's rules to combine the model parameter estimates across the imputed datasets⁴⁰.

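### The time-varying PPI and H2-blocker analysis has no exposure lag, so it is open to reverse causation, and its relation to the baseline risk equation is left unclear.

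*Protocol*

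**What the plan says.** On PPIs and H2 blockers, Protocol section 6.8.4 (Variable selection) states: "we will determine the association between risk of oesophageal cancer and type of medication (omeprazole etc"), together with "dose and duration of exposure (e.g. < 6 months; 6-11 months; 12-23 months; 24-47 months; 48 months or more"). It adds: "We will examine both usage at baseline and also as a time varying exposure during study follow-up".

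Section 6.3 follows patients until oesophageal cancer, death, leaving the practice, the study end or 15 years. Section 6.8.2 sets the risk period, for all analyses, from cohort entry to the first diagnosis date. No section mentions a lag, a latency period or the setting aside of prescriptions shortly before diagnosis.

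Three places fix predictors at entry. The medication list in section 6.6.2 is headed "concurrent medication (at study entry"). Section 6.6.4 ends: "All predictor variables will be based on the latest coded information recorded in the GP record prior to entry to the cohort". Section 6.8.3 says: "For all predictor variables, we will use the most recently available value at the time origin". Section 6.8.5 then combines the final-model coefficients with a baseline survivor function to give risk for each year up to 10 years.

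**The concern.** Section 6.6.2 describes both drug classes as treatments for reflux symptoms, and section 4.4 says PPIs might mask a developing oesophageal cancer. The protocol thus already expects some prescribing while a cancer is present but undiagnosed. If the tumour's own symptoms prompt the prescription, a time-varying exposure updated to diagnosis counts that prescription as exposure preceding the cancer, although the cancer came first. Such cases gather in the shortest-duration band.

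The one symptom safeguard, in section 6.2.3, removes patients with new alarm symptoms in the 3 months before entry. It has no effect on prescriptions started during follow-up.

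What is at stake is the reading of the PPI duration analysis. Section 4.4 names the exploration of long-term medication risks as an opportunity of the project. A high ratio in recent starters that declines with longer use could be read as a drug effect, or as a benefit of longer use, when it is neither.

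A second, smaller matter is where the analysis belongs. A coefficient for exposure after entry cannot be used directly in an equation that predicts from values known at the time origin. Yet the paragraph directly follows the rules for retaining variables in the model.

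**Working it through.** The protocol gives no figure for this bias, so there is none to reproduce. The check has a textual part and an illustration.

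**Text.** Section 6.8.4 places exposure during follow-up. Sections 6.3 and 6.8.2 end follow-up at diagnosis for cases. Nothing separates the two, so a literal reading counts a prescription issued shortly before diagnosis. Sections 6.6.2, 6.6.4, 6.8.3 and 6.8.5 all require predictors known at entry. Section 6.8.4 does not say which side of that line the time-varying analysis falls on.

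**Illustration.** Every input below is an assumption; none comes from the protocol. The true effect is set to none (ratio 1).

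*Calculation A.* Assume 1.5% of person-time lies in the first 6 months of use, and that a share s of cases start in the 6 months before diagnosis because of the tumour.

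Apparent ratio = [(s + 0.015) / (1 − s − 0.015)] / [0.015 / 0.985], with denominator 0.01523.

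- s = 1%: 0.02564 / 0.01523 = 1.7
- s = 10%: 0.12994 / 0.01523 = 8.5
- s = 20%: 0.27389 / 0.01523 = 18.0
- s = 30%: 0.45985 / 0.01523 = 30.2

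*Calculation B.* Assume non-users start at r = 0.03 per year, and that starting is k times as frequent in a symptomatic window of w years before diagnosis. Assume a background prevalence of current use p of 5% to 20%, and no stopping.

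Use under 6 months against non-use, for w of 0.5 or 1: ratio = (exp(0.5kr) − 1) / (exp(0.5r) − 1), with denominator 0.01511.

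- k = 2: 0.03045 / 0.01511 = 2.0
- k = 5: 0.07788 / 0.01511 = 5.2
- k = 10: 0.16183 / 0.01511 = 10.7

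Use begun before the window is inflated only because non-users are depleted among cases: ratio = exp((k − 1)rw).

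| k | under 6 months | 6 months or more (w = 0.5) |
|---|---|---|
| 2 | 2.0 | exp(0.015) = 1.02 |
| 5 | 5.2 | exp(0.06) = 1.06 |
| 10 | 10.7 | exp(0.135) = 1.14 |

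This is a falling duration pattern with no drug effect. With w = 1 the 6-11 month band is inflated too: (exp(kr) − exp(0.5kr)) / (exp(r) − exp(0.5r)) gives 2.0 for k = 2 and 12.3 for k = 10. Bands of 12 months or more then show between exp(0.03) = 1.03 and exp(0.27) = 1.31.

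Any current use: ratio = [(1 − u) / u] / [p / (1 − p)], where u = (1 − p)·exp(−(k − 1)rw).

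- Smallest (p = 0.20, w = 0.5, k = 2): u = 0.7881, ratio 1.08
- Largest (p = 0.05, w = 1, k = 10): u = 0.7252, ratio 7.2

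For scale, section 6.8.4 retains binary variables with a hazard ratio above 1.10, subject also to significance. In this model a lag at least as long as w returns a ratio of 1.0 by construction. A shorter lag removes only part of the bias.

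**The case against.** The strongest reply is that the protocol is silent on a lag rather than opposed to one. The analysis is named in one sentence, the duration bands are only examples, and an analysis plan that is not shown may specify a lag. That is fair, and it rules out saying that the sponsor chose to ignore latency. It does not remove the point. The exposure period and the end of follow-up are both stated, and taken together they leave recent prescriptions in.

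A reader might also infer that section 6.8.4 contradicts the rules fixing predictors at entry. The wording does not support this. The paragraph speaks of determining an association, and time-varying use is added to baseline use without replacing it. What remains is an ambiguity created by placement under variable selection.

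Third, the primary objective is prediction, and a predictor that marks early disease is not thereby wrong for prediction. This stands. The bias matters for interpreting the drug association, which is a secondary exploration. No section makes the rationalising of PPI use depend on this hazard ratio.

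Fourth, the duration bands isolate recent starters from long-term users. Calculation B largely bears this out: bands lying wholly outside the symptomatic window are only mildly inflated. The contrast between bands, however, is what a duration-response analysis reports.

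Finally, a reader might infer from the entry rule ("12 months after registering with their GP practice") that long durations at baseline are cut short for recent registrants. This cannot be checked. Section 6.6.4 refers to information in the GP record before entry and does not limit it to the current registration.

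**Conclusion.** The point holds as a vulnerability of the analysis as written. An unlagged time-varying analysis of PPI and H2-blocker use is open to reverse causation, mainly in the band under 6 months, and could produce a spurious association with a falling duration-response.

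The illustrative apparent ratio for that band is about 2 to 30 with no true effect, and 1.08 to 7.2 for any current use. These ranges rest wholly on assumed starting rates, symptomatic windows and shares of cases. They also rest on the premise that an undiagnosed tumour can prompt these prescriptions. They show that the bias could be large; they do not show that it will be.

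Whether exposure after entry could reach the risk equations is unclear rather than contradictory, and one sentence would settle it. The baseline prediction model is not shown to be invalid.

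**What to change.** 1. State in section 6.8.4 that only PPI and H2-blocker use at entry can enter the risk equations, in line with sections 6.6.2, 6.6.4, 6.8.3 and 6.8.5.
2. Describe the time-varying work as a separate, exploratory association analysis.
3. Lag the exposure in that analysis, so that prescriptions in a set period before each risk time are ignored. Twelve months is an example of a main lag, with shorter and longer lags (say 6 and 24 months) as sensitivity analyses. The protocol offers no basis for a particular length, so the sponsor should justify the choice. Stability across lags is the useful evidence.

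The cost is a little more exposure coding and the loss of recent exposure time from the association analysis. No new data are needed and the prediction models are unaffected.

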6.8.5 Risk equations

We will use the regression coefficients for each variable from the final model as weights which we will combine with the baseline survivor function evaluated for each year up to 10 years to derive risk equations over a period of 10 years of follow-up⁴¹. This will enable us to derive risk estimates for each year of follow-up, with a specific focus on 10-year risk estimates. We will estimate the baseline survivor function based on zero values of centred continuous variables, with all binary predictor values set to zero.

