2.4 Vision

To re-design and evaluate the clinical pathway such that we systematically identify those at risk, perform a simple test to inform who needs endoscopy and in so doing rationalise the use of long-term PPI medication. Due to the cost-effectiveness of Cytosponge-TFF3 compared with endoscopy these changes will likely result in an economic benefit to the NHS, a social benefit for early detection of a lethal cancer and a reduction in over-use of PPI medication.

3 Summary Work Package 1

- **Objective** To derive and evaluate a risk prediction tool to predict oesophageal cancer (all types and according to squamous or adenocarcinoma subtype) which can be applied in primary care to identify high risk patients suitable for assessment with the Cytosponge in primary care.
- Design Prospective population based open cohort study using routinely collected data from 1500 GP practices in England in the QResearch database (derived from EMIS electronic medical records) between 01.01.2000 and 31.12.2020 (or latest data available). We will use the QResearch database to develop the risk equations. Models will be developed on a derivation dataset from a subset of approximately 1100 practices and validated in the remaining 400 practices. The model will be externally evaluated in other relevant datasets as they become available.
- Subjects We will study adults aged 40 years and over who are free of oesophageal cancer at study entry. Patients with a new onset of alarm symptoms (e.g. dysphagia, weight loss etc) in the preceding 3 months will also be excluded.
- Methods Cox time-to-event models will be used in the derivation data to derive separate risk equations in males and females for estimating risk of oesophageal cancer. Predictors considered will include age, ethnicity, deprivation, smoking status, alcohol intake, body mass index, pre-existing medical co-morbidities, and concurrent medication. Measures of performance (prediction errors, calibration and discrimination) will be determined in the validation data for men and women separately and by ten-year age group.
- **Outcome** Our primary outcome is oesophageal cancer defined as recorded on GP record or linked hospital, cancer registry or death certificate.

4 Background

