4.1 Clinical need

5.1.1 Epidemiology of oesophageal cancers

Oesophageal cancer is the 8th most common cancer and one of the deadliest cancers in the world². Although oesophageal squamous cell carcinoma (OSCC) is the predominant histological type worldwide, oesophageal adenocarcinoma (OAC) is more common in developed countries such as United States, Australia, United Kingdom, and Western Europe².

Incidence of the cancer type OAC has increased 6-fold since the 1990s and carries a dismal prognosis. The UK has some of the worst outcomes from this disease in Europe. Clinical guidelines have focussed on minimising endoscopy referrals unless patients have "alarm symptoms" suggestive of cancer. Nevertheless, General Practice referral rates vary widely, and low endoscopy referral rates have been linked with poor outcomes from oesophageal cancer.

A major risk factor for this cancer is chronic heartburn caused by reflux. Three to six percent of individuals with reflux predominant symptoms may have the precursor lesion called Barrett's oesophagus, but only around 20% of patients with Barrett's are diagnosed. It is estimated that the burden of OAC could be reduced by up to 50% as a result of increasing the proportion of individuals with reflux symptoms who are investigated. This is a formidable task since heartburn symptoms affect between 5%-20% of the population and account for up to 10% of GP consultations. GPs therefore focus on controlling reflux symptoms with acid-suppressant medication, particularly proton pump inhibitor therapy (PPI). PPIs are highly effective, but patients often continue taking them life-long and there are increasing concerns about long-term side effects including osteoporosis, pneumonia^{3 4} and recently allergy³.

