6.2 Study Population

6.2.1 Practice inclusion

We will include all practices in England who had been using their EMIS computer system for at least a year. We will randomly allocate three quarters of QResearch practices to the derivation dataset and the remaining quarter to a test (validation) dataset.

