6.2.2 Patient inclusion

We will identify an open cohort of individuals aged 25-90 years who are registered with practices that have been contributing to QResearch for over 12 months on or after 1st January 2000 (study start date).

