6.8.7 Updating of the model using new data

We will update the models to ensure the model remains up to date. The baseline survivor function may change after the widespread introduction of the Cytosponge (for example), so will be updated in future models where possible³². Even though it may not be possible to fully account for changes in baseline survival over time the risk scores will give a rank ordering of patients that can be used for risk stratification/identification of high-risk groups.

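### The 10-year absolute risks average incidence over 2000-2020 with weight on the earlier years, and the planned internal calibration would not show it if incidence rose in that time

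*Protocol*

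**What the plan says.** - **Entry (6.3).** "Patients will enter the cohort on the latest of the study start date or the date on which they become 25", or 12 months after registration if that is later. Each patient has one entry date, and everyone already eligible enters on 1 January 2000. Data run to 31.12.2020, or later if available (section 3).
- **Model (6.6, 6.8.2).** Time runs from cohort entry and predictors are taken as recorded before entry. Neither calendar year nor period of entry is among the candidate predictors.
- **Risk equation (6.8.5).** The coefficients are to "combine with the baseline survivor function evaluated for each year up to 10 years to derive risk equations over a period of 10 years", with the emphasis on 10-year risk. Models are separate for men and women. Nothing restricts the baseline function to a recent period or stratifies it by period.
- **Validation (6.2.1, 6.8.6).** "We will randomly allocate three quarters of QResearch practices to the derivation dataset and the remaining quarter to a test (validation) dataset". Calibration compares predicted risk with 10-year Kaplan-Meier estimates by tenth of risk. Performance is repeated by age group and in long-term PPI users, but not by calendar period.
- **Trend (4.1, under the subheading numbered 5.1.1).** "Incidence of the cancer type OAC has increased 6-fold since the 1990s". Adenocarcinoma is one of the modelled outcomes (6.4).
- **Updating (6.8.7).** "The baseline survivor function may change after the widespread introduction of the Cytosponge", so the baseline is to be updated in future models where possible.

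**The concern.** A pooled baseline function gives the average hazard at each follow-up time over all the entry years that reach it. Patients who enter on 1 January 2000 inform the 10-year equation only through 2000-2009, and only those who enter by the end of 2010 can supply a full 10 years by 31.12.2020. If incidence changed over those years, the released figure is an average over the past, not the risk of a patient assessed now.

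The validation practices have, in expectation, the same mix of entry years as the derivation practices. Predicted and observed risk then share the same average, and overall calibration looks right whatever the trend.

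What is at stake is the absolute risk. Section 5 foresees sharing the result with patients, web tools for the public and mathematical modelling of the pathway. Section 6.9.4 envisages presenting absolute as well as relative risk. These uses need a figure that is right for the present.

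**Working it through.** The protocol gives no figure on this point, so there is none to reproduce. The calculation below shows the possible size.

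**Inputs from the protocol:** entry from 1 January 2000, data to 31 December 2020, a 10-year horizon, time origin at entry.

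**Assumptions, not in the protocol:** a share f of patients enters on 1 January 2000, with f = 30% or 50%. The rest enter evenly over the next 20 years. Loss to follow-up and case mix do not depend on entry year. Incidence grows by a constant g a year.

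**Formula.** Let incidence relative to mid-2020 be λ(t) = (1+g)^(t − 2020.5). At follow-up time u the pooled hazard is the mean of λ(entry + u) over patients whose entry + u falls before the end of data. Loss that is equal across entry years cancels. The ratio of pooled 10-year risk to risk at 2020 incidence is the average of this hazard over u = 0 to 10. The outcome is rare, so risks and cumulative hazards are nearly interchangeable.

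**Calendar centre of the baseline function, f = 50%**
- At u = 0: 2000 + 0.50 × 10 = 2005.0.
- At u = 10, of the later entrants only those from the first 11 of the 20 years remain. Their weight is 0.50 × 11/20 = 0.275 and their mean entry is 2005.5. The centre is 2010 + 0.275 × 5.5/(0.50 + 0.275) = 2011.95.
- Averaged over all u: about 2008.6.

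**Calendar centre, f = 30%**
- At u = 0: 2000 + 0.70 × 10 = 2007.0.
- At u = 10: weight 0.70 × 11/20 = 0.385, centre 2010 + 0.385 × 5.5/(0.30 + 0.385) = 2013.1.
- Averaged over all u: about 2010.2.

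The gap to 2020.5 is therefore 11.9 years (f = 50%) or 10.3 years (f = 30%).

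**Ratio of pooled 10-year risk to risk at 2020 incidence**

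| Annual growth | Approximation from the gap | Full calculation |
|---|---|---|
| 0% | 1.0 | 1.0 |
| 1% | 1.01^−11.9 = 0.89; 1.01^−10.3 = 0.90 | 0.89-0.90 |
| 2% | 1.02^−11.9 = 0.79; 1.02^−10.3 = 0.82 | 0.79-0.82 |

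**What the internal validation would show.** A random split by practice gives both sets the same expected entry-year mix. The expected overall ratio of predicted to observed risk is 1.0 in every row.

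**How far the mixture reaches.** With the same inputs, about 30-45% of the person-time in follow-up years 0-10 falls in 2010 or later.

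**Effect of a 2010 start.** Put f on 1 January 2010 and spread the rest over the following 10 years. The centre moves to about 2016.2 (f = 50%) or 2016.8 (f = 30%), gaps of 4.3 and 3.7 years. At 2% growth, 1.02^−4.3 = 0.92 and 1.02^−3.7 = 0.93.

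**The case against.** **The protocol concedes drift and relies on ranking.** Section 6.8.7 accepts that changes in baseline survival may not be fully accounted for, and says the scores still rank patients. Section 6.8.8 examines centile thresholds. A proportional rise in incidence leaves the order of patients largely unchanged, so recall by centile is little affected. This stands and limits the harm to absolute risk. It does not answer the point for the uses in sections 5 and 6.9.4, because ranking does not give a patient or a pathway model the right absolute figure. The only change 6.8.7 names lies in the future, and it leaves updating to later models.

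**Other checks are foreseen.** Section 3 plans evaluation in other datasets, and 6.9.2 says an independent evaluation should be done. It would therefore be too strong to say that no validation could reveal the problem. But no dataset or period is fixed. Section 6.7 tabulates crude incidence by calendar time as description only.

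**Three stronger readings are tempting and not supported.**
- *The risks reflect the 2000s only.* The cohort is open and brings in later person-time, so they are a mixture.
- *The cap is a cause.* Section 6.3 sets "a maximum follow up period of 15 years", but the baseline function is used only to year 10. Follow-up in years 10-15 does not enter it.
- *Adenocarcinoma risk is understated about 3-fold.* That requires spreading the 6-fold rise evenly over an assumed 25 years (6^(1/25) − 1 = 7.4% a year) and projecting it to about 2026. The protocol gives neither the time course nor the share after 2000, and it gives no trend for all types combined or for squamous cancer.

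**It could be left to the analysis plan.** A calibration table by period might be, and its absence alone would not be a finding. The entry rule, baseline function, split and calibration method are fixed in the protocol, and the point concerns those choices.

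**Conclusion.** The point holds for absolute 10-year risk. As specified, the equations describe average incidence over 2000-2020 with more weight on the earlier years, and the internal calibration would not show an error arising from a trend within that period.

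On the assumed entry pattern, the released risk relative to risk at 2020 incidence runs from 1.0 with no trend after 2000, through about 0.89-0.90 at 1% annual growth, to 0.79-0.82 at 2%. The last is an understatement of about 1.22- to 1.27-fold (1/0.82 to 1/0.79). The growth rates and entry shares are illustrative. The true trend is not in the protocol and the bias may be nil, which is a reason to check calibration by period rather than to assume a size.

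**What to change.** 1. **Section 6.8.6:** report calibration in the validation practices by calendar period of entry, for example 2000-04 and 2005-10 at 10 years, and 2011 onwards at 5 years.
2. **Section 6.8.5:** re-estimate the baseline survivor function for the released equations in a recent cohort with the same definitions, for example with study start 1 January 2010. Data to 31.12.2020 still allow 10 years of follow-up. Keep the full 2000-2020 cohort for the coefficients.

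**Cost:** one re-estimation and one stratified table, on data already held. Intervals for baseline risk become somewhat wider, which should be tolerable with the at least 18,000 cases cited in 6.8.9. The correction is partial: at 2% annual growth the ratio to 2020 incidence rises from 0.79-0.82 to about 0.92-0.93, not to 1.0.
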